5.4.3 Removal of Patient from Therapy

Reasons for permanent discontinuation of treatment include the following:

- Patient experiences two or more Grade 2 toxicities or one or more Grade 3 or 4 toxicity considered by the PI to be associated with LSALT peptide treatment (CTCAE v5.0, 2017)
- Patient requests to discontinue treatment or patient withdrawal of consent
- PI considers that it is not in the best interest of the patient to continue treatment due to an adverse event.
- Protocol deviation requiring discontinuation of study treatment for safety reasons, and/or
- Pregnancy.

Patients who discontinue treatment for any reason (except withdrawal of consent from study participation) will not be discontinued from the study and will continue to be followed for all

assessments until Day 28, or if not possible then for all assessments necessary to determine the value of the primary endpoint at Day 28.

5.4.3.1 Procedures for Early Termination of Treatment

For any discontinuation, the PI will obtain all the required details and document the date and the main reason for the premature termination. If the reason for discontinuation is an AE, the specific event or the main laboratory abnormality will be recorded in the electronic case report form (eCRF). The PI will make thorough efforts to document the outcome. The PI will attempt to continue to follow the patient for the full duration of the study and continue planned assessments. If circumstances prevent the patient from completing all scheduled evaluations, every attempt will be made to complete all procedures listed in Section 8.2.5.

6 STUDY PRODUCT

6.1 Study Medication Supply

LSALT peptide and matching placebo will be sent to the sites per the randomization schemata. Drug receipt/administration logs and temperature logs will be maintained by the study site using the Drug Accountability Form. The unblinded Pharmacist/designate will ensure that the total number of vials in the drug dispatch log is present in the shipment from the Sponsor. The Pharmacist/designate will also ensure that there is no evidence of breakage of the drug vials. The Sponsor/designate must be notified immediately if any discrepancy is identified in the drug or temperature log or if any breakage occurs.

6.1.1 Description and Formulation of Study Product

LSALT peptide will be supplied to the study site in aqueous solution at -20°C as a single concentration (1 mg/mL) in a glass vial with restricted access to the site Pharmacist or designate. The LSALT peptide vials will be labeled in English or the local language in the country of study and according to local regulations (Appendix 1).

6.1.2 Study Drug Dosage and Preparation

LSALT peptide or an equivalent volume of 0.9% sodium chloride (NaCl) will be diluted in 0.9% sodium chloride solution to a volume of 100 mL mini-IV bag by an unblinded Pharmacist or designate. The drug will be infused into the patient through a peripheral 18, 20, or 22 g intravenous catheter or through a central line over 2 hours and under the supervision of the study investigator.

6.1.3 Pharmacy records

The unblinded Pharmacist or designate will be responsible for ensuring that the study site maintains an accurate record of the LSALT peptide inventory using the Drug Accountability Form. A coded label will be affixed to the patient eCRF to identify placebo and LSALT peptide-treated subjects.

6.1.4 Conditions for Storage and Use

All study medication will be stored in the research pharmacy prior to dispensing, or in a locked freezer accessible only to the pharmacy team. Study drug (LSALT peptide and commercially-available drug-free saline) should be stored frozen at -20°C (-4°F) in a temperature-monitored

freezer; a record of daily temperatures during the study will be reviewed by the Sponsor or delegate. Refer to the Pharmacy Manual on specifics of storage and other related information.

6.2 Study Drug Administration

The dose will be one of the following for each patient:

- A. 100 mL of 5 mg IV LSALT peptide infusion over 2 hours once daily
- B. 100 mL drug-free IV saline infusion over 2 hours once daily.

The frozen study drugs (LSALT peptide or saline) will be warmed to room temperature by the unblinded Pharmacist before dispensing to the investigators for adding to the infusion bags. As warming time may vary, every effort should be made to allow ample time to the unblinded Pharmacist for the completion of the warming procedure. Post-preparation, the drug product and placebo will be stored for no longer than 4 hours at room temperature (68°F/20°C) or no longer than 24 hours when refrigerated (35°F/2°C) prior to administration to the patient to minimize the risk of excessive growth of adventitious microbial contamination. Times of post-preparation to infusion and storage temperatures will be documented in the pharmacy records and eCRF.

Study drug will be administered once daily at a consistent time throughout the study. A missed dose of study medication can be administered up to 8 hours before the next scheduled dose; otherwise, the missed dose should not be administered to the patient and the deviation should be noted on the eCRF.

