After assessing the risk of ARDS and satisfying all inclusion and exclusion criteria, the patient will be randomized to 5 mg LSALT peptide or blinded placebo to be given intravenously once daily for a maximum of 14 days. Physical and respiratory examinations, vital signs, and adverse events will be recorded throughout the study, including Day 28 (EOS). Blood chemistries, hematology, coagulation, urinalysis, ECG, SARS-CoV-2 tests, eGFR, and chest x-ray (CXR) will be assessed at Day 1 (Screening/Baseline) prior to initiation of study drug, and on Day 3, EOT, and at EOS, as well as when clinically indicated. The ECG at EOS will only be obtained if clinically indicated. An additional CXR will be obtained at time of clinical improvement. Cytokines/biomarkers and pharmacokinetics (PK) will be assessed at Day 1 (Screening/Baseline) prior to initiation of study drug, at 1 (mid-dose) and 2 hours (end of infusion) of drug therapy on Days 1, 3, EOT, and a single blood sample at EOS for cytokines/biomarkers only. Where applicable, a urinary pregnancy test will be obtained at Screening in women of childbearing potential. Questionnaires (APACHE II, SOFA) will be obtained at Baseline, Day 3, EOT, and EOS; venous blood gas (VBG) or HCO₃ (bicarbonate) levels may be substituted for arterial blood gas (ABG) if it is considered standard-of-care (SOC) or in the patient's best interest, and results in comparable APACHE II and SOFA scores. Other questionnaires (Berlin Definition and modified Medical Research Council Dyspnea Scale) will be assessed at Baseline, Day 3, EOT, and EOS. IgG, IgA, and IgM antiviral antibodies will be collected at Baseline and EOS. Patients will be maintained on the SOC per institutional guidelines, including prophylaxis or treatment of VTE, throughout the study.

A Data and Safety Monitoring Board (DSMB) will evaluate patients on a continuing basis for primarily safety assessments. Per the DSMB Charter, the DSMB will meet at least monthly if not more frequently based upon enrollment throughout the study period.

NUMBER OF PATIENTS (PLANNED): Thirty (30) patients will be randomized to active drug (LSALT peptide) and 30 patients will be randomized to matching placebo. This study will be third-party blind with only the Pharmacist at the site unblinded for the purpose of preparing drug/placebo for injection.

DIAGNOSIS AND MAIN CRITERIA FOR INCLUSION:

Key Inclusion Criteria:

Eligible patients must fulfill the following inclusion criteria:

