 - Ulinastatin 200,000 IU or greater
 - High dose intravenous Vitamin C
 - Budesonide and formoterol
 - Bevacizumab to prevent ARDS
 - Dornase alfa to reduce hypoxemia in ventilated trauma patients.
7. As indicated in the inclusion criteria, pregnant female patients are excluded from study. Further, female patients who are nursing are excluded from study.
8. Has any medical condition considered to be clinically significant and could potentially affect patient safety or study outcome, including but not limited to:
 - Acute or chronic kidney disease (stage-4 or -5 renal impairment; eGFR <30 mL/min/1.73 m² or hemodialysis)
 - End-stage malignancy undergoing treatment
 - Immunocompromised patients or those with medical/surgical conditions (*e.g.*, solid organ transplantation) which require chronic immunosuppression

- Chronic hematologic disease which, in the opinion of the PI, prohibits the patient from entering into study
- Acute liver injury with AST and/or ALT levels greater than 3x ULN, unless recent injury (within 2 weeks) likely due to COVID-19 infection
- History of coagulopathy of unknown etiology, as defined by abnormal ACT (only if part of SOC), aPTT, and/or PT/INR values at least 2-fold outside normal limits, and currently present at screening, and/or
- End-stage lung disease, acute lung injury, very severe chronic obstructive pulmonary disease (COPD) as assessed by the GOLD criteria (GOLD Stage IV), or mechanical ventilation.

TEST PRODUCT, DOSE, AND MODE OF ADMINISTRATION:

LSALT peptide or an equivalent volume of commercially-available 0.9% sodium chloride (saline) solution to a volume of 100 mL mini-IV bag by an unblinded Pharmacist or designate. The drug will be infused into the patient through a peripheral 18, 20, or 22 g intravenous catheter over 2 hours and under the supervision of the Principal Investigator. Study drug may also be administered through a central line. Study drug will be administered once daily at a consistent time throughout the study.

DURATION OF TREATMENT: Maximum of 14 days.

DISCONTINUATION FROM TREATMENT:

Reasons for permanent discontinuation of treatment include the following:

- Patient experiences two or more Grade 2 toxicities or one or more Grade 3 or 4 toxicity considered by the PI to be associated with LSALT peptide treatment (CTCAE v5.0, 2017)
- Patient requests to discontinue treatment or patient withdrawal of consent

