5.2 Number of Patients (Planned)

Thirty (30) patients will be randomized to active drug (LSALT peptide) and 30 patients will be randomized to matching placebo. Patients and, if necessary, the Legal Authorized Representative (LAR), the Investigational Staff, and the Sponsor and its representatives will not know the randomization schemata. The Pharmacist at the site will be unblinded and prepare drug/placebo for injection.

A Data and Safety Monitoring Board (DSMB) will evaluate patients on a continuing basis for primarily safety assessments but also the adequacy of treatment based upon clinical data of the patient, target drug concentrations, and data obtained from the AB001 PK study in healthy subjects to offer recommendations to the Sponsor. In the absence of adverse events or any safety issues during the course of study, the DSMB may recommend continuance or suspension of the study due to futility or safety issues. The DSMB will meet at least monthly if not more frequently based upon enrollment throughout the study period. Per protocol, at no time will patients be dosed for more than 14 days of therapy. The DSMB Charter will outline all processes for changes to the protocol and protocol design prior to the first patient being enrolled into study.

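### Section 6.2 has investigators add the thawed product to the infusion bag, while section 6.1.2 and the synopsis give that step to an unblinded pharmacist or designate

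*Combined protocol and SAP*

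**What the plan says.** Section 6.2, Study Drug Administration, says the frozen LSALT peptide or saline "will be warmed to room temperature by the unblinded Pharmacist before dispensing to the investigators for adding to the infusion bags". The investigators therefore fill the bag.

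Section 6.1.2, Study Drug Dosage and Preparation, gives the same step to someone else: "LSALT peptide or an equivalent volume of 0.9% sodium chloride (NaCl) will be diluted in 0.9% sodium chloride solution", and this is done "to a volume of 100 mL mini-IV bag by an unblinded Pharmacist or designate". The synopsis, under Test Product, Dose, and Mode of Administration, names the same operator ("solution to a volume of 100 mL mini-IV bag by an unblinded Pharmacist or designate"), although its sentence lacks a verb.

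Two further places set out the blinding without mentioning the bag. The synopsis, under Number of Patients, describes a third-party blind "with only the Pharmacist at the site unblinded for the purpose of preparing drug/placebo for injection". Section 5.2 says "The Pharmacist at the site will be unblinded and prepare drug/placebo for injection", and that among others "the Investigational Staff, and the Sponsor and its representatives will not know the randomization schemata".

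**The concern.** The trial is double-blind, and the blind rests on an unblinded pharmacist preparing the infusion so that everyone else sees only a finished bag. If investigators receive the unmixed product and add it themselves, that barrier is gone and masking depends on whatever container and label they are handed.

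Three things could be affected if an investigator learned the arm:

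- **Causality ratings.** Under section 7.3.1.2 these decide which adverse events count as related. They feed the tables by attribution in section 9.3.4.1 and the relationship tables in the synopsis.
- **Stopping treatment.** Section 5.4.3 makes toxicity that the principal investigator attributes to LSALT a ground for permanent discontinuation.
- **Later assignments.** Section 6.2.2 specifies fixed blocks in a 1:1 ratio, so known assignments could make later ones easier to guess. How much easier depends on the block size, which is not stated.

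Safety assessment is one of the stated grounds for the sample size in section 9.1, so investigator attribution is not a side issue in this trial.

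**Working it through.** This is mainly a comparison of texts. The protocol gives no figure to reproduce.

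**Step 1. Who fills the bag?**

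| Place | Person who adds product to the bag |
|---|---|
| Section 6.2 | Investigators, after the pharmacist has thawed the product and dispensed it |
| Section 6.1.2 | Unblinded pharmacist or designate |
| Synopsis, Test Product | Unblinded pharmacist or designate |

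The step is the same and the people differ.

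**Step 2. Could the investigators be the designate?** In section 6.1.2 the designate shares the unblinded preparation role. Putting investigators in that role conflicts with the synopsis, which leaves only the pharmacist unblinded, and with section 5.2, which keeps investigational staff from knowing the randomization. This reading moves the contradiction elsewhere without removing it.

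**Step 3. Which version does the rest of the protocol support?** Section 6.1.1 restricts LSALT vial access to the pharmacist or designate. Section 6.1.4 keeps study medication in the research pharmacy or in a freezer that only the pharmacy team can open. The paragraph in section 6.2 that contains the disputed clause goes on to say "Times of post-preparation to infusion and storage temperatures will be documented in the pharmacy records and eCRF", which fits preparation in pharmacy. The clause therefore looks like a drafting slip, but no other sentence in the protocol overrides it.

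**Step 4. Would the volume reveal the arm?** The dose is 5 mg (section 6.2) and the concentration is 1 mg/mL (section 6.1.1).

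- LSALT before dilution: 5 mg ÷ 1 mg/mL = 5 mL.
- Placebo before dilution: an equivalent volume (section 6.1.2) = 5 mL.
- Difference between arms: 5 − 5 = 0 mL.

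Volume does not distinguish the arms. Container or label might, and the documents do not allow that to be checked.

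**Step 5. How far does the clause reach?** It applies to every patient, 30 + 30 = 60, and to every infusion. The ceiling is 60 × 14 = 840 infusions, if every patient received the maximum 14 daily doses.

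**The case against.** The strongest reply is that this is a stray clause, outweighed by the rest of the protocol. The disputed act is preparation, and the section whose title covers preparation, 6.1.2, gives it to pharmacy. The synopsis, section 5.2 and the access limits in sections 6.1.1 and 6.1.4 point the same way, and section 6.1.4 refers sites to a Pharmacy Manual that may already settle the matter. A site that reads the whole protocol would probably do the right thing.

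Masking may also survive a handover. Saline is frozen and thawed in the same way as LSALT (sections 6.1.4 and 6.2), the placebo is called matching (sections 5.2, 6.1 and 6.2.2), and coded identification appears in sections 6.1.3 and 6.2.3. Nor do the documents say that the person who fills the bag is the person who rates causality.

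Much of this stands. It supports reading the clause as a slip and rules out any claim that blinding has been lost. It does not reconcile the text. Section 6.2 is where site staff look for how to give the drug, and followed literally it breaks the blinding arrangement. Parallel freezing and coded records do not establish that the containers handed over are indistinguishable: section 6.1.1 describes LSALT in a labelled glass vial, and section 6.1.4 describes the placebo as commercially available saline. A sound Pharmacy Manual would lower the practical risk and still leave the protocol contradicting itself.

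**Conclusion.** The contradiction is real, is in the current text and is not resolved elsewhere in the protocol. It should be corrected before sites rely on section 6.2. Confidence is high for the textual conflict. The consequence is a risk whose size cannot be computed, because it depends on container and label masking, on who actually fills the bag and on the content of the Pharmacy Manual.

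The reach is limited. Patients who stop treatment, other than by withdrawing consent, are still followed to Day 28 (section 5.4.3). The full analysis set keeps treatment as randomized (section 9.2.1). Overall adverse event incidence does not depend on attribution (section 9.3.4.1). The documents do not say who decides the need for ventilation or oxygen in the primary endpoint, so no conclusion is drawn about that endpoint.

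**What to change.** Amend section 6.2 to agree with section 6.1.2:

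- Delete the words that send the thawed product to the investigators for addition to the bags.
- State that the unblinded pharmacist or designate prepares the bag and dispenses only the finished 100 mL bag, labelled with the patient number from section 6.2.1 and without treatment identity.
- Confirm that the Pharmacy Manual cited in section 6.1.4 says the same.

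The cost is one sentence and one document check. The unblinded pharmacist role already exists, so no staff are added, and the randomization schedule, drug supply and dose are unchanged.

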6.2.1 Patient Numbering

Each patient will be assigned a unique 6-digit patient number by the study staff. The patient number will consist of a 3-digit clinical investigational site number assigned by the Sponsor, followed by a 3-digit patient number (*e.g.*, 001) assigned by the study staff.

The clinical site and/or pharmacy, if applicable, is responsible for maintaining a current log of patient number assignments and bottle numbers of the investigational product administered to each patient. The patient's unique patient number is required to be entered on all clinical investigation documentation (*i.e.*, eCRFs, labeling of clinical materials and samples containers, drug accountability logs, *etc.*).

6.2.2 Method of Assigning Patients to Treatment Groups

This is a double-blind, placebo-controlled study. The actual treatment given to individual patients is determined by a randomization schedule. A fixed block randomization schedule will be prepared to assign patients to 1 of 2 treatments: LSALT peptide 5 mg once daily or matching placebo in a 1:1 allocation ratio.

6.2.3 Dispensing, Compliance and Accountability

The study drug must be used only as directed in the protocol. The Pharmacist/delegate will keep accurate records of the quantities of the study drug dispensed/distributed, used, and returned by each patient in the eCRF system.

The Sponsor or delegate will provide drug product accountability forms to assist the Pharmacist/delegate, when applicable, in maintaining current and accurate inventory records

covering receipt, dispensing, and the return of study drug supplies. When a shipment is received, the Pharmacist will verify the quantities received and return the acknowledgment to the Arch Biopartners Clinical Trial Material (CTM) Coordinator. The drug product will not be used without Arch Biopartners or designate approval in writing. The unblinded Pharmacist will record study drug accountability which includes the coded identification of the patient to whom the study drug is dispensed, the quantity and the date of dispensing, and any returned or unused study drug, as well as a full record of CTM storage temperatures. This record is in addition to any study drug accountability information recorded on the eCRF. These records will be readily available for inspection by an unblinded monitor and/or Arch Biopartners audits and are open to regulatory authority inspection at any time.

Noncompliance is defined as receiving less than 80% or more than 120% of study drug during the study period. Noncompliance should be discussed with the Project Manager, or delegate, and is to be noted both in the source documentation and in the eCRF.

At the end of the study, all unused study drug will be destroyed on site according to site procedures. If the site does not have procedures in place for on-site destruction, the study drug will be returned to the Arch Biopartners CTM Coordinator or designate for destruction.

Based on entries in the site electronic study drug accountability forms, it must be possible to reconcile study drug delivered with those used and returned. All study drug must be accounted for and all discrepancies investigated and documented appropriately.

The unblinded Pharmacist is responsible for maintaining accountability for the receipt, dispensing, and return of all study medication to the clinic.

6.3 Prior and Concomitant Therapy

Medications having the potential to interfere with the evaluation of efficacy or safety are excluded throughout the trial (review Sections 5.4.1 Inclusion criteria and 5.4.2 Exclusion criteria). Current therapies which have been shown to be efficacious and are included in standard COVID-19 treatment guidelines (*e.g.*, WHO or US NIH, institutional guidelines) are permitted if not part of another investigational study. All concomitant medication usage needs to be documented in the eCRF.

7 EFFICACY AND SAFETY ASSESSMENTS

7.1 Efficacy Assessments

7.1.1 Primary Efficacy Endpoint

The primary efficacy endpoint is the proportion of subjects alive and free of respiratory failure (*e.g.*, need for non-invasive or invasive mechanical ventilation, high flow oxygen [≥ 6 L/minute], or ECMO) and free of the need for continued renal replacement therapy (RRT) on Day 28. The need for continued RRT at Day 28 will be defined as either dialysis in the past 3 days (Day 26, 27, or 28) or an eGFR on Day 28 <10 mL/min/1.73 m².

7.1.2 Secondary Efficacy Endpoints

- All-cause mortality

- The presence and severity of ADRS as an ordinal outcome of the proportion of patients who have none, mild, moderate, or severe ARDS
- Time to each of mild, moderate, and severe ARDS
- The number of ventilation-free days and ECMO-free days
- Time on nasal canula or oxygen mask
- Length of stay in ICU and hospital (admission to discharge)
- Virologic clearance rate
- Worst PaO₂/FiO₂ ratio following enrollment
- Change in PaO₂/FiO₂ ratio
- Vasopressor-free days
- Change from maximal radiographic damage to EOT
- Change in baseline mMRC score
- Change in APACHE II score
- Proportion of patients with extrapulmonary organ dysfunction using the daily SOFA score
- Change in liver function tests (ALT, AST, total bilirubin)
- Change in renal function tests (SCr, eGFR)
- Change in hs-troponin levels
- Change in ACT, aPTT, and/or PT/INR values
- Change in antiviral IgG, IgA, and IgM levels.

